2.5 Study Flowchart

2.6 Study Procedures

Visit 1 (Screening and Enrollment up to the day of surgery)

- Review of medical record
- Informed Consent - Patients will be identified during their preoperative appointment and introduced to a study; they will be provided with a copy of the consent document and information about the study. The consenting will take place after additional discussion on the day of surgery.

Visit 2 (Randomization and Treatment – day of surgery)

- Anesthetic management will include rocuronium, sevoflurane, and sugammadex at the discretion of the attending anesthesiologist as per standard of care practice.
- Patients will be randomized to be monitored with TetraGraph device on either the dominant or nondominant hand. NMBA administration will be at the discretion of the anesthesiologist. Reversal with sugammadex will be based on manufacturer dosing recommendations. The TetraGraph will record data throughout the operation and into the PACU stay.
- TetraGraph monitor placed prior induction of anesthesia and the values will be used to guide care. The TetraGraph will record data throughout the operation and into the PACU stay.
- Following recirculation of the transplanted liver, the attending anesthesiologist will declare whether the patient is a fast-track candidate or not. If the patient is not a fast-track candidate, they will be considered screen failure. If they are deemed to be a fast-track candidate, their participation continues. The attending anesthesiologist can change their mind at any time and remove 'fast-track' status as the clinical situation evolves.
- At the conclusion of the operation, the patient will be reversed with sugammadex as per standard of care practice and manufacturer's dosing recommendations.
- The patient's trachea will be extubated at the discretion of the attending anesthesiologist as per routine practice.
- Upon arrival to the recovery room for patients in both groups, two sets of train-of-four ratio (TOFR) will be obtained. If these values are more than 20% different, a third set will be obtained. Measurements will be obtained in a similar fashion 5 minutes and 10 minutes into the recovery room stay. If any TOFR < 0.9, the attending anesthesiologist will be notified as to intervene if medically appropriate.
- The patient's electronic medical record will be reviewed for up to 30 days postoperatively. Patient characteristics such as age, gender, albumin level, type of surgery, and baseline glomerular filtration rate will be recorded.

Schedule of Events		
Study Activity	Visit 1	Visit 2
TetraGraph/Peripheral Nerve Stimulator		X
Sugammadex		X
Informed consent	X	
Review of Medical Record	X	X
Adverse event evaluation		X

| **2.7 Study Duration** | Subject participation will be 3-6 hours, depending on duration of surgery. The entire study will be completed within 2 years based on the total number of eligible patients. | |
| **2.8 Statistical Analysis and Sample Size Justification** | This is an open-label investigation. Masking and blinding procedures are not applicable. **Sample Size Determination** Assuming the incidence of postoperative weakness incidence with sugammadex without quantitative monitoring is 46% (9) and the incidence of weakness with sugammadex and a quantitative monitor is 5% (11), 28 patients would be required to be powered (80% power, $p<0.05$) to show evidence of a reduction in residual weakness with the use of quantitative monitoring to below 46%. However, we will consent up to 100 patients to account for possible dropouts and missing data to meet target accrual of 30 patients. **Statistical Methods** Continuous variables will be summarized as mean (standard deviation) or median (range) while categorical variables will be reported as frequency (percentage). For the primary aim, we will calculate the proportion of patients who have postoperative weakness, expressed as a percentage; we will perform a one-sample binomial test of the null hypothesis that the true proportion is 46%, and we will calculate an exact binomial 95% confidence interval (CI) for the true proportion of postoperative weakness for patients who are fast tracked. For the first secondary aim, we will similarly calculate the proportion of patients who go to the ICU, expressed as a percentage along with a 95% CI for the true proportion. For the second secondary aim we will calculate the sample mean length of stay of the patients in the study along with a 95% CI – due to the skewness of the distribution of length of stay we will construct a bootstrap-based CI. For the third secondary aim, we will calculate the proportion of patients who have postoperative | |

complications along with a 95% CI. We will also summarize the frequencies of patients with each particular complication type.

Handling of Missing Data

This is a prospective study and therefore we do not anticipate any missing data. In the event of any unexpected missing data, no attempt to impute this missing data will be made; missing data will simply be treated as missing in the statistical analysis, and replacement participants will be enrolled to achieve the target accrual of n=30 participants.

Subject Population for Analysis

Each participant who undergoes surgery and completes neuromuscular monitoring will be included in the primary analysis regardless of study withdrawal for any reason. In the event of any study withdrawals, in secondary analysis we will examine the sensitivity of our results to the exclusion of patients who withdrew.

Intraoperative Data

Study ID:				
Examiner Initials:				Date (dd / mm / yyyy):
Dominant side: Hand with TetraGraph on		L / R L / R		Age (yrs)
Weight (kg):		Height (cm):		BMI:
Muscle relaxant name:				
Muscle relaxant total dose (mg):				
Time of last muscle relaxant dose (mm : hh):		: am / pm		
Reversal agent name:				
Reversal agent dose (mg):				
Time of reversal agent administration (mm : hh):		: am / pm		

	
Cardiac output at time of reversal administration:
 
 
 Time of extubation:	:	am / pm	
 
 	
 
 TOFC and TOFR (if TOFC = 4) prior to extubation					
 
 TOFC and TOFR (if TOFC = 4) at time of extubation					
 
 TOFC and TOFR (if TOFC = 4) on arrival to PACU					
 
 TOFC and TOFR (if TOFC = 4) 5 min after PACU arrival					
 
 TOFC and TOFR (if TOFC = 4) 10 min after PACU arrival					
 
				Time of extubation:	:	am / pm								TOFC and TOFR (if TOFC = 4) prior to extubation					TOFC and TOFR (if TOFC = 4) at time of extubation					TOFC and TOFR (if TOFC = 4) on arrival to PACU					TOFC and TOFR (if TOFC = 4) 5 min after PACU arrival					TOFC and TOFR (if TOFC = 4) 10 min after PACU arrival				
Time of extubation:	:	am / pm																																					
TOFC and TOFR (if TOFC = 4) prior to extubation																																							
TOFC and TOFR (if TOFC = 4) at time of extubation																																							
TOFC and TOFR (if TOFC = 4) on arrival to PACU																																							
TOFC and TOFR (if TOFC = 4) 5 min after PACU arrival																																							
TOFC and TOFR (if TOFC = 4) 10 min after PACU arrival																																							
2.9 Specific Drug Supply Requirements	
All drugs used in the course of providing medical care for the 30 patients will be supplied by the participating institution in this protocol.
																																						
2.10 Adverse Experience Reporting	
Safety and Adverse Events
 
Definitions
 
Unanticipated Problems Involving Risk to Subjects or Others (UPIRTSO)
 
Any unanticipated problem or adverse event that meets the following three criteria:
 
 • Serious: Serious problems or events that results in significant harm, (which may be physical, psychological, financial, social, economic, or legal) or increased risk for the subject or others (including individuals who are not research subjects). These include: (1) death; (2) life threatening adverse experience; (3) hospitalization - inpatient, new, or prolonged; (4) disability/incapacity - persistent or significant; (5) birth defect/anomaly; (6) breach of confidentiality and (7) other problems, events, or new information (i.e. publications, DSMB reports, interim findings, product labeling change) that in the opinion of the local investigator may adversely affect the rights, safety, or welfare of the subjects or others, or substantially compromise the research data, AND • Unanticipated: (i.e. unexpected) problems or events are those that are not already described as potential risks in the protocol, consent document, or not part of an underlying disease. A problem or event is "unanticipated" when it was unforeseeable at the time of its occurrence. A problem or event is "unanticipated" when it occurs at an increased frequency or at an increased severity than expected, AND • Related: A problem or event is "related" if it is possibly related to the research procedures. 
Adverse Event
 
An untoward or undesirable experience associated with the use of a medical product (i.e. drug, device,
																																						

biologic) in a patient or research subject.

Serious Adverse Event

Adverse events are classified as serious or non-serious. Serious problems/events can be well defined and include;

- death
- life threatening adverse experience
- hospitalization
- inpatient, new, or prolonged; disability/incapacity
- persistent or significant disability or incapacity
- birth defect/anomaly

and/or per protocol may be problems/events that in the opinion of the sponsor-investigator may have adversely affected the rights, safety, or welfare of the subjects or others, or substantially compromised the research data.

All adverse events that do not meet any of the criteria for serious, should be regarded as **non-serious adverse events**.

Adverse Event Reporting Period

For this study, the follow-up period is defined as up to 10 minutes after arrival to PACU or TOFR is ≥ 0.9 (whichever occurs first).

Preexisting Condition

A preexisting condition is one that is present at the start of the study. A preexisting condition should be recorded as an adverse event if the frequency, intensity, or the character of the condition worsens during the study period.

Post-study Adverse Event

All unresolved adverse events should be followed by the sponsor-investigator until the events are resolved, the subject is lost to follow-up, or the adverse event is otherwise explained. At the last scheduled visit, the sponsor-investigator should instruct each subject to report, to the sponsor-investigator, any subsequent event(s) that the subject, or the subject's personal physician, believes might reasonably be related to participation in this study.

Hospitalization, Prolonged Hospitalization or Surgery

Any adverse event that results in hospitalization or prolonged hospitalization should be documented and reported as a serious adverse event unless specifically instructed otherwise in this protocol. Any condition responsible for surgery should be documented as an adverse event if the condition meets the criteria for an adverse event.

Neither the condition, hospitalization, prolonged hospitalization, nor surgery are reported as an adverse event in the following circumstances:

- Hospitalization or prolonged hospitalization for therapy of the target disease of the study, unless it is a worsening or increase in frequency of hospital admissions as judged by the clinical investigator.

Recording of Adverse Events

At each contact with the subject, the study team must seek information on adverse events by specific questioning and, as appropriate, by examination. Information on all adverse events should be recorded immediately in the source document, and also in the appropriate adverse event section of the electronic case report form (CRF). All clearly related signs, symptoms, and abnormal diagnostic, laboratory or procedure results should be recorded in the source document.

All adverse events occurring during the study period must be recorded. The clinical course of each event should be followed until resolution, stabilization, or until it has been ultimately determined that the study treatment or participation is not the probable cause. Serious adverse events that are still ongoing at the end of the study period must be followed up, to determine the final outcome. Any serious adverse event that occurs during the Adverse Event Reporting Period and is considered to be at least possibly related to the study treatment or study participation should be recorded and reported immediately.

Reporting of Serious Adverse Events and Unanticipated Problems

When an adverse event has been identified, the study team will take appropriate action necessary to protect the study participant and then complete the Study Adverse Event Worksheet and log. The sponsor-investigator will evaluate the event and determine the necessary follow-up and reporting required.

Sponsor-Investigator reporting: notifying the Mayo IRB

The sponsor-investigator will report to the Mayo IRB any UPIRTSOs and NonUPIRTSOs according to the Mayo IRB Policy and Procedures. Each participating site will report SAEs to their respective IRB or Ethics Committee with copy of submission and review provided to the leading site. Should there be any SAEs at any of the participating sites; the study team at that site will notify the primary site (Mayo Clinic in Florida) within 24 hours of learning of the event.

Any serious adverse event (SAE) which the Principal Investigator has determined to be a UPIRTSO will be reported to the Mayo IRB as soon as possible but no later than 5 working days after the investigator first learns of the problem/event.

The following information will be collected on the adverse event worksheet (and entered in the research database):

- Study ID
- Disease
- The date the adverse event occurred
- Description of the adverse event
- Relationship of the adverse event to the research device*
- Determination if the adverse event was expected
- The severity of the adverse event (severity scale described below **)
- If any intervention was necessary
- Resolution (was the incident resolved spontaneously, or after discontinuing treatment)
- Date of Resolution

The sponsor-investigator will review all adverse event reports to determine if specific reports need to be made to the IRB. The sponsor-investigator will sign and date the adverse event report when it is reviewed. For this protocol, only directly related SAEs/UPIRTSOs will be reported to the IRB.

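### The stated 28 patients for 80% power (46% versus 5%) does not follow from the planned one-sample binomial test, which needs 9 or 10; the figure equals a two-arm total of 2 × 14

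*Combined protocol and SAP*

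**What the plan says.** Under Sample Size Determination, section 2.8 assumes 46% weakness with sugammadex alone, and continues that if "the incidence of weakness with sugammadex and a quantitative monitor is 5% (11), 28 patients would be required to be powered", with 80% power and p<0.05. The stated aim is to "show evidence of a reduction in residual weakness with the use of quantitative monitoring to below 46" per cent. The plan then allows up to 100 consents so that 30 patients are accrued.

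Under Statistical Methods, the same section sets the primary analysis: "we will perform a one-sample binomial test of the null hypothesis that the true proportion is 46" per cent, with an exact binomial 95% confidence interval. It does not state sidedness, the sample-size formula or the software.

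Section 2.6 describes the only randomisation: "Patients will be randomized to be monitored with TetraGraph device on either the dominant or nondominant hand". Every patient has the quantitative monitor and is to be reversed with sugammadex, so no group is managed without quantitative monitoring.

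**The concern.** The plan gives the null rate, the alternative, the significance level, the power and the test, so the figure of 28 can be checked without any outside source. The gap between 46% and 5% is very large, and a one-sample test against a fixed value should need far fewer than 28 patients to detect it.

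If 28 and 80% do not belong to the planned test, the plan has no valid justification for its size. A reader would take n=30 as just adequate to detect 5% against 46%, and would not learn what 30 patients can and cannot show. The wrong power statement could also carry into the manuscript planned in section 2.13, where a referee entering the plan's own inputs could not reproduce it.

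**Working it through.** **Inputs, all from section 2.8:** p0 = 0.46, p1 = 0.05, alpha = 0.05, power 80%, stated n = 28, target n = 30. Sidedness is not given, so both were tried.

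**1. Where 28 can come from.** The formula for two independent proportions with unpooled variance, two-sided, is

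n per arm = (1.960 + 0.842)² × (0.46×0.54 + 0.05×0.95) / (0.46 − 0.05)²
= 7.849 × (0.2484 + 0.0475) / 0.1681 = 13.8,

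so 14 per arm and 28 in total. This matches the plan exactly. Other two-arm methods, two-sided, give different totals:

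| Two-arm method | Per arm | Total |
|---|---|---|
| Unpooled | 14 | 28 |
| Arcsine | 15 | 30 |
| Pooled | 17 | 34 |
| Fisher exact | 19 | 38 |
| Pooled, continuity-corrected | 22 | 44 |

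**2. What the planned one-sample test needs.** The normal approximation, two-sided, is

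n = [1.960 × √(0.46×0.54) + 0.842 × √(0.05×0.95)]² / 0.41²
= (0.977 + 0.183)² / 0.1681 = 8.01, so 9.

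The exact binomial test gives:

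| n | Version | Reject if weak ≤ | Lower-tail probability at 46% | Power at 5% |
|---|---|---|---|---|
| 9 | one-sided, or two-sided minimum-likelihood (p = 0.0445) | 1 | 0.0338 | 92.9% |
| 10 | two-sided, doubled tail | 1 | 0.0201 | 91.4% |
| 28 | two-sided | 7 | 0.0189 | 99.995% |
| 30 | one- or two-sided | 8 | 0.0243 | 99.999% |

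For n=10 the power can be checked by hand: 0.95¹⁰ + 10 × 0.05 × 0.95⁹ = 0.5987 + 0.3151 = 0.914.

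Across normal, continuity-corrected, null-variance and exact versions, one- and two-sided, the required number is 6 to 12 at 80% power and at most 16 at 90% power. None gives 28.

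**3. What 80% power corresponds to.** For the two-sided exact test, power is 80% at a true incidence of about 20% with n=28 (80.1% at 20.45%), and about 22% with n=30 (80.05% at 22.05%).

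**4. What n=30 gives for estimation.** Exact 95% confidence intervals:

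| Weak patients | 95% CI |
|---|---|
| 0/30 | 0 to 11.6% |
| 1/30 | 0.1 to 17.2% |
| 2/30 | 0.8 to 22.1% |

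The test rejects 46% at up to 8/30 = 26.7% observed weakness, more than five times the hypothesised ceiling of 5%. Conversely, even no events in 30 would not exclude a true rate above 5%.

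**The case against.** The strongest reply is that the error is harmless. The trial has more patients than its test needs; if the true rate is near 5%, rejection of 46% is practically certain. The study is called a pilot, its primary objective is estimation, and an exact confidence interval is already planned. All of that is true, and it limits the damage to the justification: test, interval and enrolment stand. It does not make the printed number and power right, and a pilot aimed at estimation has all the more reason to state its expected precision.

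The second reply is that the two-arm origin is conjecture. The plan gives no formula and no per-arm figure, and the match depends on the unpooled version. A one-sample calculation also yields 28 if the true rate is 20% (exact, two-sided, power 81.8%). This stands: the origin cannot be settled from the documents. But the plan names 5%, not 20%, and the finding that 28 and 80% do not belong to the planned test does not depend on where 28 came from.

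The third reply is that sidedness is unstated and should not be assumed. At n=28 it matters: the one-sided rule is 8 or fewer, the two-sided rule 7 or fewer. At the target of n=30 the rule is 8 or fewer either way, so the corrected figures hold for both.

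**Conclusion.** The concern holds. Under the plan's own inputs the one-sample test needs 9 or 10 patients for 80% power, so 28 is about three times the requirement. Power at 28 or 30 exceeds 99.9%. The stated number equals a two-arm total of 2 × 14, a design this trial does not have; that this formula was actually used is an inference.

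The conclusion rests on the printed 46%, 5%, 0.05 and 80%, on 30 analysed patients, and on the one-sample test as written; it does not depend on sidedness. The error is conservative and does not threaten the primary test. It should nevertheless be corrected, because the sole sample-size statement for the primary endpoint is wrong and does not explain the choice of 30.

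**What to change.** Replace the power sentence in section 2.8 with figures that belong to the planned test, and state the sidedness. Suggested wording, if two-sided is intended:

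*With 30 patients, the two-sided exact one-sample binomial test at the 5% level rejects an incidence of 46% if 8 or fewer patients have residual weakness. Power exceeds 99.9% if the true incidence is 5% and is 80% if it is about 22%.*

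Then justify 30 by precision, which suits the estimation objective: *The exact 95% confidence interval would be 0 to 11.6% with no weak patients, 0.1 to 17.2% with one, and 0.8 to 22.1% with two.* Add that 30 patients cannot confirm a rate below 5%. If the sponsor did use a two-arm calculation, any mention of it should be dropped or explained.

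The cost is one paragraph of wording, with no change to enrolment, procedures or analysis.

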*** Relationship Index**

	
The relationship of an AE to the Investigational Device is a clinical decision by the sponsor-investigator (PI) based on all available information at the time of the completion of the eCRF and is graded as follows:
 
 1. Not related: a reaction for which sufficient information exists to indicate that the etiology is unrelated to the use and proper application of study device. 2. Unlikely: a clinical event, including laboratory test abnormality, with a temporal relationship to use of the study device which makes a causal relationship improbable and in which use of other devices, chemicals, or underlying disease provide plausible explanations. 3. Possible: a clinical event, including laboratory test abnormality, with a reasonable time sequence to use of the study device but which could also be explained by concurrent disease or use of other devices or chemicals. 4. Probable: a clinical event including laboratory test abnormality, with a reasonable time sequence to use of the study device, unlikely to be attributed to concurrent disease or use of other devices or chemicals. 5. Definite: a reaction that follows a reasonable temporal sequence from the use of the study device. 
** Severity Scale
 
The maximum intensity of an AE during a day should be graded according to the definitions below and recorded in details as indicated on the CRF. If the intensity of an AE changes over a number of days, then separate entries should be made having distinct onset dates.
 
 1. Mild: AEs are usually transient, requiring no special treatment, and do not interfere with patient's daily activities. 2. Moderate: AEs typically introduce a low level of inconvenience or concern to the patient and may interfere with daily activities, but are usually ameliorated by simple therapeutic measures. 3. Severe: AEs interrupt a patient's usual daily activity and traditionally require systemic drug therapy or other treatment.
2.11 Itemized Study Budget	
A preliminary study budget must be provided with the initial proposal submitted to give guidance to the MISP Review Committee as to the expected study costs. A refined itemized budget detailing the costs associated with the study should be provided with the final protocol or included in the study agreement as Exhibit B.

